3.2 General study level definitions

3.2.1 Relative day and time

For each participant, the relative day of an event or assessment will be derived using the earliest date of their first dose of UCB6114 as reference.

Relative days for an event or assessment occurring before the date of the first dose are calculated as follows:

$$\text{Relative Day} = \text{Event/Assessment Date} - \text{Date of First Dose of UCB6114}$$

The relative day for an event or assessment occurring on the date of first dose is 1. The relative day for an event or assessment occurring on or after the first dose to the date of the last dose of UCB6114 will be calculated as follows:

$$\text{Relative Day} = (\text{Event/Assessment Date} - \text{Date of First Dose of UCB6114}) + 1$$

For events or assessments occurring after the date of the last dose of UCB6114, relative day will be prefixed with '+' in the data listings and will be calculated as follows:

$$\text{Relative Day} = \text{Event/Assessment Date} - \text{Date of Last Dose of UCB6114}$$

There is no relative Day 0. Relative day will not be calculated in cases where dates are partial and should be presented as “--” in the relevant data listing.

Relative time of TEAEs recorded on, but not limited to, the day of UCB6114 infusion, will be derived in minutes as follows using the infusion start time as reference:

Relative Time of TEAE = Onset Time of TEAE – Start Time of UCB6114 Infusion

Relative times of PK and PD sampling will be derived in hours using the end of infusion times on the day of UCB6114 dosing as reference:

Relative Sampling Time = Sampling Time – End Time of UCB6114 Infusion

3.2.2 Study periods

Part A1 of the study will consist of the following study periods:

- Screening Period – up to 28 days;
- Treatment Period – Successive 28-day cycles for Cohorts 1, 2, and 4, and 21-day cycles for Cohort 3. UCB6114 is administered as iv infusion as per defined dosing schedules until the occurrence of progressive disease, unacceptable toxicity, or withdrawal of consent;
- Safety Follow-up Period – up to 30 days after the last dose of UCB6114.

There will be a further extended follow-up period, up to 3 months after the last dose of UCB6114, at which time the Final Visit will be performed.

For each participant, the end of the Treatment Period is defined by the date of their last dose of UCB6114.

The end of Part A1 of the study is defined by the date of the Final Visit for the last participant (3 months after the last participant’s last dose of UCB6114), or the date of the SFU visit, if they discontinue prior to attending the Final Visit, or their last contact date if they discontinue early from the study without attending the SFU visit.

3.2.3 Visits

Unless otherwise specified, in the TFLs, visits will be labelled as follows (as applicable) using timepoints as recorded in the database:

Screening
Baseline
Cycle 1, Day X
Cycle 2, Day X
Cycle 3, Day X
Cycle 4, Day X
Cycle X, Day X
Etc.
SFU
Final Visit

3.3 Definition of Baseline values

Baseline in Part A1 will be the last available value prior to the first dose of UCB6114. Both scheduled and unscheduled values, as well as any repeated values, should be used when defining Baseline.

Measurement-specific Baseline definitions are presented in [Table 3-1](#) below.

Table 3-1: Definition of Baseline

Measurement	Definition of Baseline
Echocardiogram (LVEF) Tumor assessments (antitumor activity) Tumor biopsy (Ki67, SMAD4, FAP, pSMAD1/5/8)	Screening value
12-lead ECG Physical examination and weight Vital signs Clinical laboratory data ECOG performance status	Predose value obtained on Cycle 1, Day 1, or, if missing, Screening value
Circulating gremlin-1 (cGremlin-1) Immunogenicity (ADA)	Predose sample value obtained on Cycle 1, Day 1

ADA=anti-drug (UCB6114) antibody; ECG=electrocardiogram; ECOG=Eastern Cooperative Oncology Group; LVEF=left ventricular ejection fraction.

3.4 Protocol deviations

Per ICH definition, important protocol deviations (IPDs) are a subset of protocol deviations that may significantly impact the completeness, accuracy, and/or reliability of the study data or that may significantly affect a participant's rights, safety, or well-being. The criteria for identifying potentially important protocol deviations will be defined within the IPD specifications document.

For Part A1 of this study, IPDs will be categorized as follows:

- Inclusion/exclusion criteria deviations;
- Incorrect treatment or dose administered;
- Procedural non-compliance;
- Prohibited concomitant medication use (see Section 6.5.6 of the protocol);
- Withdrawal criteria deviation.

All protocol deviations will be reviewed as part of the ongoing data cleaning process and Data Evaluation Meetings (DEMs), and decisions made on whether they should be considered important or not, and whether they warrant a participant's exclusion from an analysis set, or partial exclusion from an analysis due to being an IPD (e.g. prohibited concomitant medication use). Multiple DEMs will be scheduled prior to the final database lock for Part A1, in line with

regulatory safety reporting requirements, with the final one held after all data have been verified/coded/entered into the database.

More specifically, participants who have IPDs relating to dosing of UCB6114 (e.g. interrupted, discontinued and missed infusion, incomplete/incorrect dose administered, additional dose received, or infusions administered outside of the defined visit window) will be reviewed at the DEM for potential exclusion of UCB6114 concentration data from the by-visit summaries at an individual visit or from the visit at which the dosing deviation was observed onwards.

Any protocol deviations that are considered related to coronavirus disease 2019 (COVID-19) will be reviewed on an ongoing basis in case they collectively or individually give reason to consider a protocol amendment (e.g. study design changes or changes to primary analysis methods etc.). To facilitate this ongoing review, protocol deviations will be categorized as ‘related to COVID-19’ within the Clinical Trial Management System (CTMS) (ICOTrial). The COVID-19-related IPDs will then be listed separately for review and discussion at the DEMs.

3.5 Analysis sets

Study participants will be analyzed according to the dose, frequency of dosing and duration of infusion they actually received regardless of which treatment group they were assigned to.

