2.3 Study design and conduct

Study ONC001 is a multicenter, nonrandomized, open-label, Phase 1/2 study evaluating the safety, PK, efficacy (as assessed by antitumor activity), PD, biomarkers, and immunogenicity (ADA activity) of intravenous (iv) UCB6114 as monotherapy and in combination with selected standard of care (SOC) regimens in study participants with advanced solid tumors.

The study has a modular design including up to 3 dose escalation modules (Parts A, B, and C), 1 dose optimization module (Part A1), and up to 4 dose expansion modules (Parts D, E, F, and G). Depending on emerging data, not all modules may open. This SAP is focused only on the dose optimization module of the study to evaluate alternative dosing schedules for UCB6114 administered as monotherapy in participants with unresectable locally advanced or metastatic colorectal adenocarcinoma, gastric adenocarcinoma, adenocarcinoma of the gastroesophageal junction, or pancreatic adenocarcinoma.

Part A1 consists of a Screening Period, Treatment Period (consisting of 28-day cycles for Cohorts 1, 2, and 4, and of 21-day cycles for Cohort 3), a SFU visit and a Final Visit. During the Treatment Period, UCB6114 will be administered as iv infusion as per the defined dosing

schedules in Table 6-6 of the protocol until the occurrence of progressive disease, unacceptable toxicity, or withdrawal of consent.

Part A1 will be initiated after Cohort 5 of Part A (2000mg every 2 weeks [Q2W]) has been determined to be safe (i.e. DLT incidence <33%, see Section 4.1.2.4 of the protocol). Eligible participants with unresectable locally advanced or metastatic colorectal adenocarcinoma, gastric adenocarcinoma, adenocarcinoma of the gastroesophageal junction, or pancreatic adenocarcinoma will receive iv infusion of UCB6114 as monotherapy.

[figure not shown]
The planned dose optimization scheme for Part A1 will assess the safety and tolerability of the new drug formulation and will explore shortening of the infusion time and less frequent dosing as follows:

- Cohort 1: 2000mg Q2W (60-minute iv infusion), 28-day treatment cycle
- Cohort 2: 2000mg Q2W (30-minute iv infusion), 28-day treatment cycle
- Cohort 3: 3000mg every 3 weeks (Q3W) (90-minute iv infusion), 21-day treatment cycle
- Cohort 4: 4000mg every 4 weeks (Q4W) (120-minute iv infusion), 28-day treatment cycle

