3.6 Treatment assignment and treatment groups

In Part A1, it is planned that study participants will be dosed with UCB6114 to evaluate a new dose formulation, different frequencies of dosing (e.g. Q3W, Q4W), and different durations of infusion. Treatment groups will be defined by each UCB6114 dose schedule cohort and will be presented in ascending cohort number order and labelled in the TFLs as illustrated in [Table 3-2](#).

Table 3-2: Treatment Group Labels

UCB6114 Dose Schedule Cohort	Planned Treatment Group Label
Cohort 1	UCB6114 2000mg Q2W (60-min), 28D
Cohort 2	UCB6114 2000mg Q2W (30-min), 28D
Cohort 3	UCB6114 3000mg Q3W (90-min), 21D
Cohort 4	UCB6114 4000mg Q4W (120-min), 28D

min=minutes; Q2W=every 2 weeks; Q3W=every 3 weeks; Q4W=every 4 weeks; 21D=21-day cycle; 28D=28-day cycle.

UCB6114 dose schedule cohort will be referred to as ‘treatment group’ from this point onwards in the SAP and in the TFLs.

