8.1 Extent of exposure

Details on UCB6114 administration on Day 1 (all cohorts) and Day 15 (Cohort 1 and 2 only) of each cycle will be listed. This listing will be split into two parts. The first part will include the start and stop dates and times of infusion, duration of infusion, infusion rate, whether the infusion was temporarily stopped/interrupted, whether the infusion was permanently discontinued and, if this was the case, whether the interruption or permanent discontinuation was due to an AE or other reason. The second part of this listing will include, for each visit, infusion site, total volume delivered, volume infused, planned total dose and total dose actually administered at infusion. In addition, the percentage of planned dose received, total dose administered across all cycles, the number of complete cycles of UCB6114 received and the total number of doses of UCB6114 received will be listed.

The percentage of planned dose received will be calculated for UCB6114 for each study participant at each dosing visit within each cycle as follows:

$$\text{Percentage of Planned Dose Received} = 100 \times \frac{\text{Total Dose Administered}}{\text{Planned Total Dose}}$$

Actual duration of infusion will be calculated in minutes only for those study participants who did not have any temporary interruption(s) of their infusion using the infusion start and stop times and included on this listing. Length of interruption(s) will be calculated in minutes for those study participants who had temporary interruption(s) of their infusion.

Extent or duration of exposure will be calculated and summarized. Frequency counts and percentages for the number of complete cycles of UCB6114 received (0, 1, 2, 3, 4, >4) and summary statistics for the total dose of UCB6114 received across all cycles, the total number of doses of UCB6114 received and the duration of exposure to UCB6114 will be presented.

Total duration of exposure will be calculated in days as follows:

$$\text{Total Duration of Exposure} = (\text{Date of Last Dose} - \text{Date of First Dose}) + 30$$

Note that 30 days is added to this calculation to account for a participant's continued exposure to UCB6114 following their last dose of study treatment.

Note that the definition of a participant deemed to have completed a full cycle of UCB6114 is given in [Section 5.1](#).

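### Part A1 groups participants by the infusion actually received, with no limit to allocation errors, so a Cohort 2 infusion slowed by a reaction can be tabulated in Cohort 1

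*SAP*

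**What the plan says.** Part A1 is meant to assess a new formulation and "will explore shortening of the infusion time and less frequent dosing" (section 2.3). Two of its four cohorts matter most here. One is given as "Cohort 1: 2000mg Q2W (60-minute iv infusion), 28-day treatment cycle". The other, which differs from it only in infusion time, is given as "Cohort 2: 2000mg Q2W (30-minute iv infusion), 28-day treatment cycle". The remaining two are 3000 mg every 3 weeks over 90 minutes (Cohort 3) and 4000 mg every 4 weeks over 120 minutes (Cohort 4).

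The grouping rule stands at the head of section 3.5, so it governs every analysis set: "Study participants will be analyzed according to the dose, frequency of dosing and duration of infusion they actually received regardless of which treatment group" was assigned. Section 3.6 adds that "Treatment groups will be defined by each UCB6114 dose schedule cohort and will be presented in ascending cohort number order" and gives the planned label for each cohort. Section 8 presents the safety outputs by treatment group on the Safety Analysis Set, and section 3.5.2 admits participants to that set after a partial dose.

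The plan expects adverse events to alter infusions. Section 8.1 lists interruptions and permanent discontinuations with their reason, and section 8.2 tabulates events that led to an interruption or a lower dose. The section of the same number in the Part A SAP has no as-received sentence.

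**The concern.** Infusion duration, dose received and dosing interval can all be consequences of how well the drug was tolerated. If they also decide the group, membership can depend on the outcome being tabulated. The sharpest case is Cohort 2 against Cohort 1, because infusion time is the only planned difference between them and a reaction can lengthen an infusion. At stake is the attribution of treatment-emergent events, dose-limiting toxicities and infusion-related reactions to the schedule that produced them. For the shorter infusion, that attribution is what the comparison of these two cohorts is for.

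**Working it through.** **Step 1. Which changes match another cohort's description?** The cohort definitions are from sections 2.3 and 3.6.

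| Change during treatment | What was received | Matching cohort |
|---|---|---|
| Cohort 2 infusion slowed to about 60 min | 2000 mg Q2W, 60 min | Cohort 1 |
| Cohort 1 or 2 dose cut | less than 2000 mg Q2W | none |
| Cohort 1 or 2 dosing delayed to 3 weeks | 2000 mg at 3 weeks | none |
| Cohort 3 infusion slowed to 120 min | 3000 mg Q3W, 120 min | none |
| Cohort 4 dose cut to 3000 mg | 3000 mg Q4W | none |

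Only the first row is a clear move from one cohort to another. In the others the rule gives no destination. It is also silent on a participant whose infusions differ from each other.

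**Step 2. Effect on observed rates.** Input: 8 participants per cohort (section 2.4). The numbers of reactors are assumptions, because the SAP gives none.

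Moving one reactor turns x/8 into (x−1)/7 in the cohort of origin and y/8 into (y+1)/9 in the receiving cohort. (x−1)/7 < x/8 whenever x < 8, and (y+1)/9 > y/8 whenever y < 8. A reaction-driven move therefore lowers the first rate and raises the second, except when all 8 have reacted.

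| Assumed case | Cohort 2 | Cohort 1 |
|---|---|---|
| No move | 2/8 = 25.0% | 0/8 = 0% |
| One reactor moved | 1/7 = 14.3% | 1/9 = 11.1% |
| Both reactors moved | 0/6 = 0% | 2/10 = 20.0% |
| One non-reactor moved | 2/7 = 28.6% | 0/9 = 0% |

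The last row runs the other way: if an infusion overruns for a reason unrelated to a reaction, Cohort 2 looks worse. In another assumed case, 3/8 = 37.5% becomes 2/7 = 28.6% after one reactor is moved, which crosses the 33% maximum tolerable rate in section 2.4.

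**Step 3. The plan's own probability.** Section 2.4 states 80% for declaring a cohort too toxic when Part A1 is taken independently of Part A. No cut-off is stated; at least 2 of 8 at a 33% rate reproduces it:

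1 − 0.67^8 − 8 × 0.33 × 0.67^7 = 1 − 0.0406 − 0.1600 = 0.799.

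If exactly one participant with a dose-limiting toxicity is counted elsewhere, 3 must occur for 2 to remain:

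0.799 − 28 × 0.33² × 0.67^6 = 0.799 − 0.276 = 0.524 (to rounding).

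This shows how sensitive a count in 8 participants is to one reassignment. It is not the operating characteristic of the trial's monitoring, because nothing in the SAP says that regrouping enters that review.

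**Step 4. Can actual duration be obtained?** Section 8.1 derives actual duration only for infusions without a temporary interruption. It also lists start and stop times and calculates the length of interruptions, so elapsed time is recoverable. What the plan lacks is a statement of which duration, elapsed or net of interruptions, would count as the one received.

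**The case against.** The best defence is that section 3.5 states the ordinary as-treated convention. It contrasts assignment with receipt, and it names dose, frequency and duration because those features define the cohorts. Other sections fit that reading. Section 8.1 reports the percentage of planned dose received, and section 8.2 tabulates event-driven interruptions and reductions by group, which presumes that these participants still have one. Sections 3.4 and 7 treat altered infusions as dosing deviations, reviewed for their effect on concentration data and analysis sets, with no mention of reassignment. This may well be the intent. What stands against it is that no section restricts the rule to allocation errors, so two programmers could build different primary safety tables from the same data.

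A reader might infer more than the documents support:

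- **That 3.5 contradicts 3.6.** It does not. Section 3.6 defines the groups and gives planned labels; section 3.5 says how participants are placed in them.
- **That the rule cannot be applied to interrupted infusions.** The times needed are listed; the derivation is incomplete, not impossible.
- **That the bias must favour the shorter infusion.** This holds for prolongation caused by a reaction. An overrun for another reason can push the other way.
- **That dose decisions are compromised.** The Safety Monitoring Committee works from the DLT Evaluable Set, sentinel review and ad hoc review after any dose-limiting toxicity (sections 2.3, 3.5.7 and 4.7). Individual reactions are also flagged in the adverse event listing.

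**Conclusion.** The point holds in limited form. As written, section 3.5 permits grouping that depends on the outcome. The one clear transfer is from Cohort 2 to Cohort 1 through a slowed infusion; reduced, cut or delayed dosing mostly leaves the group undefined. When a reaction causes the transfer, the schedule that produced it shows a lower event rate: on assumed counts, 25.0% against 0% becomes 14.3% against 11.1% after one move. The reversal to 0% against 20.0% needs two reactors, both finishing near 60 minutes and both regrouped. These sizes rest on assumed numbers of reactions and on literal application of the sentence. The exposure is in the final descriptive by-group safety tables, much less in ongoing monitoring.

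**What to change.** Replace the sentence in section 3.5 of the Part A1 SAP with wording such as:

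> Participants are analysed in the dose schedule cohort whose planned regimen was started at the first infusion. Interruptions, rate changes, dose reductions and delays do not change the group. As-received grouping applies only to a participant given another cohort's planned regimen in error, for reasons unrelated to an adverse event.

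In section 8.1, derive total elapsed infusion time, including interruptions, for every infusion from the start and stop times already listed, and show it beside the planned time. Event-driven departures then stay visible within the cohort in which they arose.

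The cost is a wording change, the treatment variable in the analysis datasets and one added derivation. It needs no new data and changes no dosing or clinical rule. It should be settled before the final database lock for Part A1.

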3.5.1 Enrolled Set (ES)

The Enrolled Set (ES) consists of all study participants who sign the Informed Consent Form.

This analysis set includes screening failures and will be used for the summary of disposition of study participants and for selected data listings (which will include all available data for the screening failures).

3.5.2 Safety Analysis Set (SS)

The Safety Analysis Set (SS) consists of all study participants who receive at least 1 full or partial dose of UCB6114.

This analysis set will be used for the reporting of demographic, baseline characteristics, safety and immunogenicity data. All summaries of the exploratory antitumor activity endpoints will be repeated for the SS as a sensitivity analysis.

3.5.3 Per-protocol Set (PPS)

The Per-protocol Set (PPS) consists of all study participants in the SS who do not have IPDs that may substantially affect antitumor activity. Potential exclusions will be reviewed at the DEMs and a final determination of the composition of this analysis set will be made prior to the final database lock for Part A1.

The PPS will be the primary analysis set for the analysis of the exploratory antitumor activity endpoints.

3.5.4 Pharmacokinetic Set (PKS)

The Pharmacokinetic Set (PKS) consists of all study participants in the SS who have at least 1 evaluable postdose UCB6114 concentration sample (i.e. a sample which is above the lower limit of quantitation and for which the date and time of the sample and prior date and time of dosing are known). Additional participants or specific samples may be excluded from the PKS at

the discretion of the Advanced Modeling and Simulation scientist/Quantitative Clinical Pharmacologist at UCB.

Pharmacokinetic analysis will be performed for the PKS.

3.5.5 Anti-drug Antibody Set (ADAS)

The Anti-drug Antibody Set (ADAS) consists of all study participants in the SS who have at least 1 evaluable ADA assessment (i.e. a sample that has a reported result [is not missing or inconclusive]).

Immunogenicity analyses will be performed for the ADAS.

3.5.6 Pharmacodynamic Set (PDS)

The Pharmacodynamic Set (PDS) consists of all study participants in the SS who have at least 1 evaluable PD assessment (where appropriate, the sample should be above the lower limit of quantitation and the date and time of the sample should be known).

Pharmacodynamic analyses will be performed for the PDS.

3.5.7 DLT Evaluable Set (DES)

The DLT Evaluable Set (DES) will include all study participants who, during the 28-day DLT Observation Period, receive the planned dose of UCB6114.

The DES will be used only for evaluations by the SMC to determine if a dosing schedule and Part A1 can continue as planned.

3.6 Treatment assignment and treatment groups

In Part A1, it is planned that study participants will be dosed with UCB6114 to evaluate a new dose formulation, different frequencies of dosing (e.g. Q3W, Q4W), and different durations of infusion. Treatment groups will be defined by each UCB6114 dose schedule cohort and will be presented in ascending cohort number order and labelled in the TFLs as illustrated in [Table 3-2](#).

Table 3-2: Treatment Group Labels

UCB6114 Dose Schedule Cohort	Planned Treatment Group Label
Cohort 1	UCB6114 2000mg Q2W (60-min), 28D
Cohort 2	UCB6114 2000mg Q2W (30-min), 28D
Cohort 3	UCB6114 3000mg Q3W (90-min), 21D
Cohort 4	UCB6114 4000mg Q4W (120-min), 28D

min=minutes; Q2W=every 2 weeks; Q3W=every 3 weeks; Q4W=every 4 weeks; 21D=21-day cycle; 28D=28-day cycle.

UCB6114 dose schedule cohort will be referred to as ‘treatment group’ from this point onwards in the SAP and in the TFLs.

